## Suubi4Her Proposal

Final Version: 7-September-2017

**Study Overview.** The Suubi4Her program will test the effects of a combination asset-based financial inclusion intervention (YDAs) with an evidence-based family strengthening intervention to be delivered via multiple family groups (MFG) to understand the effects and costs associated with a combined intervention versus YDA alone. Specifically, the proposed study addresses three study aims:

**Aim 1.** Examine whether the *Suubi4Her* intervention is effective in protecting adolescent girls against known HIV risk factors (including economically-motivated sex and intimate partner violence).

**Aim 2.** Elucidate the effects of the *Suubi4Her* intervention on behavioral health functioning (i.e., depression, self-efficacy and hopelessness) and examine the effects of these variables as potential mechanisms of change, mediating the relationship between each intervention and HIV risk reduction.

**Aim 3.** Evaluate the cost-effectiveness of each intervention condition.

To address the three aims guiding the proposed study, we will randomize girls (at the school level) to one of three study conditions: 1) YDA condition with a 1:1 saving incentive match rate – for educational purposes and microenterprise development (n=420 participants; n=14 schools); 2) YDA + MFG intervention condition (n=420 participants; n=14 schools); 3) A control condition receiving standard health and sex education provided in schools (n=420 participants; n=14 schools). We detail the three study arms below.

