**Matched Savings Accounts (YDA) Intervention.** The Suubi4Her matched savings account will be in the form of a Youth Development Account (YDA), where savings are housed at a local bank and deposits made by the adolescent and family are matched, up to a match cap, by the intervention to encourage savings. Each adolescent assigned to a YDA group will receive a YDA held in her own name in a financial institution registered by the Central Bank (Bank of Uganda). We have partnered with Centenary Rural Development Bank and DTB Bank to host the YDAs. Any of the adolescent's family members, relatives, or friends will be allowed and encouraged to contribute towards the YDA. The account will then be matched with money from the study. The maximum family contribution to be matched by the program will be an equivalent of US\$10 per month (in Uganda shillings) per family or US\$240 for the 24-month intervention period. Girls who save the maximum amount will have a total of \$480 at the end of the intervention (\$240 in savings plus \$240 from the match: a 1:1 match).

Each month, a bank account statement will be generated for every girl to note her accumulated savings. Also, during the intervention period, each girl, with her primary caregiver as a co-signer, will have access to the money in her account (excluding the matching funds). This option is provided in case of an emergency (for example, a family illness). Participants can withdraw their own money—but not the matching funds. When the girls turn 18, they will no longer need co-signers. The matching funds will be kept in a separate account from the participants' own savings. When a girl is ready to pay for school fees, the check for the matching funds will be written in the name of the school she attends. Alternatively, the matching funds may be wire transferred directly to the school's bank account. The student will then contribute her portion of the total cost for the academic term out of her savings account—for which she will be a signatory. The same will apply to girls who want to invest a portion in small business development: the check will be written to the vendor for the wire transfer for the match will be

[figure not shown]

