sent directly to the vendor with the required particulars of the participant). The accounts will be monitored by Drs. [name] (PI) and [name] (in-country Co-I), assisted by the project coordinator and financial manager in Uganda. Experience with our earlier studies indicates the accounts are easy to monitor through monthly bank statements. A participant's access to the matching funds is conditional upon completion of 12 financial management workshops over 12 months.

The matched savings accounts include financial management (FM) workshops and an IGA promotion component. The FM workshops, to be implemented by our collaborating community agency (RTY-Uganda) in collaboration with the financial institutions holding the YDAs, will consist of 12 general workshops that will: a) introduce participants to the notion of asset-building; b) cover asset-building strategies in detail, e.g., saving and investing in IGAs; c) cover specific topics related to saving, e.g., the importance of saving and how it can be done. There will also be asset-specific trainings following the general FM workshops.

**Combination Intervention: Youth Development Accounts (YDA) + Multiple Family Groups (MFG).** This arm is intended to directly address both the economic needs of the participating adolescent girls as well as their mental health functioning. This combination arm tests whether combining two evidence-based interventions will reduce HIV risk over and above a financial intervention (YDA) or usual care alone. The combined arm will consist of: a) a family monetary savings program using Youth Development Accounts (YDA) (detailed above), and b) a family-based dialogue and training via Multiple Family Groups (MFGs) focused on strengthening family relationships and mental health challenges which frequently accompany adolescent girls' transition to adulthood.

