Girls in the combination intervention group (YDA + MFG) will receive: 1) a monetary savings account in the form of a YDA, matched at a rate of 1:1. The YDA will operate exactly the same way as in a YDA-only group—detailed above; 2) in addition to the YDA, each girl will also be invited, together with her caregiving family, to attend 18 60-minute MFG sessions, over the course of 18 months, to be hosted within the community. The 18 sessions include an introductory session and a program evaluation session. Each session will involve 6-12 families. The MFG curriculum will incorporate broad conceptual categories targeting family-level issues and concerns that may impact families' abilities to incorporate new behaviors. Each session will provide numerous opportunities for family members to discuss the realities of family life, as well as perspectives on culture and values, specifically those related to gender. Content is intended to foster both within and between family interaction, learning and communication. Sessions will be facilitated by trained community-level Lay Counselors composed of priests, village health care workers and community extension workers. Training of Lay counselors and having them facilitate the MFG is intended to ensure intervention fidelity, and build capacity to sustain the intervention for the community at study end.

**Usual Care: Health and Sex Education and HIV Prevention Curriculum in Secondary Schools.** Two curriculums will be delivered in all our participating secondary schools: Life Planning Skills and Adolescent Sexual Reproductive Health. All enrolled participants, both in control and treatment conditions, will be exposed to these curriculums. Specifically, the content related to HIV and sexual risk-taking behaviors will include delaying sex; using condoms and contraception; preventing forced sex; and preventing substance abuse. This curriculum will also include education on gender equality. The content will primarily be delivered via lecture. Generally, Adolescent Sexual Reproductive Health content is and will be dispersed across a range of academic subjects in secondary schools. In each class, students tend to receive information about sexual activity, HIV prevention, and gender relevant topics. Prior to study

implementation, we will hold induction meetings for all teachers involved in the study to ensure uniform delivery of this bolstered usual care.

[figure not shown]

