**Primary analyses for Specific Aim 2.** For Specific Aim 2, *Elucidate the effects of the Suubi4Her interventions on behavioral health functioning (i.e., depression, self-efficacy and hopelessness) and examine the effects of these variables as potential mechanisms of change, mediating the relationship between each intervention and HIV risk reduction*, we hypothesize that following baseline participants in:

1. H2A: YDA will have higher mean mental health functioning vs. control participants;
2. H2B: YDA+MFG will have higher mean mental health functioning vs. control participants, and
3. H2C: YDA+MFG will have higher mean mental health functioning vs. YDA participants.

[figure not shown]
The same GEE-based approach as described above in the primary analysis for Specific Aim 1 will be used to test H2A-H2C, except that instead of the odds of a binary outcome being estimated, the GEEs for H2A-H2C will employ appropriate distributions and link functions suitable for modeling the means of continuous mental health outcomes (e.g., normal distribution and identity link function). Robust Huber-White "sandwich" standard errors will be used to obtain correct inferences even if the chosen correlation structure remains slightly misspecified or if residual distributions are not perfectly normal or homoscedastic.

**Aim 3: Evaluate the cost-effectiveness of each intervention condition.** Following standard practice of measuring cost-effectiveness of interventions, we will measure costs on a per person basis. The intervention costs will include all program costs, including not just the YDA savings match, but also all costs incurred for running the program. Research costs will not be included. Data on the savings match costs will be readily available from the management information system. Data on costs of other program elements will be drawn from project administrative records and collected throughout the intervention period. In the analyses, costs from multiple years will be adjusted for inflation, depreciation, and discounting.

We will estimate how much *Combined Intervention (YDA + MFG)* vs *YDA-alone* increased particular outcomes, such as schooling. The per-person costs of *YDA + MFG*, and *YDA alone* will then be divided by the relevant effect sizes to produce estimates of cost-effectiveness.

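### Aim 3 ties no comparator or effect scale to its cost-effectiveness ratios and does not commit to the incremental ratio for adding MFG to YDA

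*Combined protocol and SAP*

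**What the plan says.** The Aim 3 text, in Data Analysis Plan and Statistical Procedures, puts costs on a per-person basis and counts all programme costs, "including not just the YDA savings match, but also all costs incurred for running the program". Research costs are left out. Match costs come from the management information system. For the rest, "Data on costs of other program elements will be drawn from project administrative records".

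Two sentences then define the analysis. The first says the team will estimate how much YDA+MFG, compared with YDA alone, "increased particular outcomes, such as schooling". The second says the per-person costs of YDA+MFG and of YDA alone "will then be divided by the relevant effect sizes to produce estimates of cost-effectiveness".

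Four other places bear on how to read this:

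- Study Overview gives the purpose as understanding the "effects and costs associated with a combined intervention versus YDA alone".
- The Combination Intervention section says of the account in the combined arm: "The YDA will operate exactly the same way as in a YDA-only group". It also says the arm tests whether the combination will "reduce HIV risk over and above a financial intervention (YDA) or usual care alone".
- The Usual Care section gives the school curricula to every arm.
- Design and Methods lists three contrasts: the two active arms against each other, and each against usual care.

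**The concern.** A cost-effectiveness ratio is interpretable only when its cost and its effect are measured against the same comparator. Aim 3 puts an arm's whole programme cost on top and leaves the effect below it undefined. The contrast it names just before is one between the two active arms, and YDA is delivered in both.

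What is at stake is the overview's own question: what adding MFG to YDA costs for what it gains. The plan does not commit to a figure that answers it. As written, two analysts could report different ratios from the same data, and could settle comparator, outcome and scale after seeing the results.

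**Working it through.** **Notation.** C_Y and C_C are the observed per-person programme costs of YDA and YDA+MFG, and D = C_C − C_Y. E_Y and E_C are their effects against usual care, signed so that positive is benefit. The incremental ratio for adding MFG is D/(E_C − E_Y).

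**Inputs.** Aim 3 states no cost, effect or ratio, so there is no result to reproduce. The only per-girl programme cost figure in the documents is the match limit in the Matched Savings Accounts section ("The maximum family contribution to be matched by the program"): US$10 × 24 months = US$240. That is a cap on one component, not a programme cost. Every other figure below is an assumption.

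**Reading 1: the denominator is the named contrast, E_C − E_Y.** The YDA+MFG ratio is C_C/(E_C − E_Y). Divided by the incremental ratio, this gives C_C/D = 1 + C_Y/D. The factor exceeds 1 whenever YDA costs something and the combined arm costs more. With D assumed at US$50, US$100 or US$200:

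| C_Y | D = 50 | D = 100 | D = 200 |
|---|---|---|---|
| 120 (half the cap) | 170/50 = 3.4 | 220/100 = 2.2 | 320/200 = 1.6 |
| 240 (the cap) | 290/50 = 5.8 | 340/100 = 3.4 | 440/200 = 2.2 |
| 400 (cap plus assumed running costs) | 450/50 = 9.0 | 500/100 = 5.0 | 600/200 = 3.0 |

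The YDA-alone ratio would be C_Y/(E_C − E_Y): the cost of YDA over a gain that YDA alone did not produce. It has no interpretation.

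**Reading 2: each denominator is against usual care.** The ratios are C_Y/E_Y and C_C/E_C. Usual care is given in all arms, so its cost approximately cancels and both ratios are valid against it. They do not fix the increment. Suppose the reported ratios are US$2,400 (YDA) and US$2,800 (YDA+MFG), with C_Y = US$240, so that E_Y = 240/2,400 = 0.1000:

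| D | E_C = (240 + D)/2,800 | E_C − E_Y | D/(E_C − E_Y) |
|---|---|---|---|
| 50 | 290/2,800 = 0.10357 | 0.00357 | US$14,000 |
| 100 | 340/2,800 = 0.12143 | 0.02143 | US$4,667 |
| 200 | 440/2,800 = 0.15714 | 0.05714 | US$3,500 |

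The same pair of reported ratios fits all three rows. A reader could separate them only if arm costs or effects were reported too.

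Nor do the two ratios settle the choice of arm. In the D = 100 row YDA has the lower ratio. At an assumed value of US$6,000 per unit of effect, net benefit is 6,000 × 0.1000 − 240 = US$360 for YDA and 6,000 × 0.12143 − 340 ≈ US$389 for YDA+MFG, so the order reverses.

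**Scale.** Aim 1 hypotheses are stated in odds and Aim 2 hypotheses in means, so an effect size has no single meaning across the plan. Take an assumed odds ratio of 0.6 and an assumed cost of US$340:

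- At 5% control risk the risk difference is 0.0194 and the cost per unit is US$17,537.
- At 40% control risk the risk difference is 0.1143 and the cost per unit is US$2,975.
- On the log-odds scale the figure is 340/0.511, about US$666, at either risk. It is not a cost per case averted.

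**The case against.** The best defence is that usual care is the natural comparator. The aim concerns each intervention condition, effect sizes is plural, Design and Methods lists both contrasts with usual care, and the alternative makes half the planned output meaningless. I accept that reading as the more plausible one, and on it neither ratio is wrong. A reader might infer from the first table that the plan will overstate cost-effectiveness ratios by 1.6 to 9.0 times. The documents do not support that: those factors apply only to Reading 1, with assumed costs.

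A reader might also infer that Aim 3 names no comparator. It does name one, in the preceding sentence. What is missing is the link from a comparator to each denominator, and the one named cannot serve YDA alone.

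Three further objections have force:

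- Identical account rules do not guarantee identical match payments, because family sessions could change how much girls save. For that reason D is defined here as the observed cost difference between arms, not as a stand-alone MFG price.
- The spread from US$3,500 to US$14,000 follows from holding two invented ratios fixed. It shows only that two ratios do not determine the third.
- The incremental ratio needs one subtraction and one division on quantities already planned. That keeps the remedy cheap, but the plan still does not commit to it.

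It might also be said that two ratios against a common comparator at least rank the arms. For choosing between them they do not do so reliably, as the net-benefit example shows.

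**Conclusion.** The point holds as a matter of specification and omission, and should be fixed. Aim 3 does not say which comparator or scale belongs to each ratio. On neither reading does it commit to the cost per unit gained by adding MFG, which the overview's stated purpose requires.

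On the literal reading the mismatch factor is C_C/(C_C − C_Y), above 1 for any positive YDA cost when the combined arm costs more. On the more plausible reading the reported ratios are correct against usual care but incomplete. The documents do not support a numerical size for either, because they give no programme cost for an arm, no MFG cost and no expected effect.

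Only Aim 3 is affected. The Aim 1 and Aim 2 tests do not depend on it.

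**What to change.** Replace the last sentence of Aim 3 with two specified ratios:

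- (a) For adding MFG: (C_YDA+MFG − C_YDA)/(E_YDA+MFG − E_YDA), using observed per-person programme costs in each arm.
- (b) For each active arm: its per-person programme cost divided by its effect against usual care.

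For each ratio, name the outcome, the comparator and an absolute effect scale, such as a marginal risk difference for a named HIV-risk outcome or a natural unit for schooling. Where the incremental effect is zero or negative, report the cost and effect differences instead of a ratio.

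The cost is SAP wording and minor extra analysis. A marginal risk difference is an added step, because the plan models odds for binary outcomes. So is a schooling effect against usual care, which Aim 3 does not currently mention. The figure for MFG may turn out less favourable. Conduct and data collection do not change.
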